Pre-Treatment Assessment (2 hours in person): Following informed consent, insomnia diagnosis will be confirmed based on a structured clinical sleep disorder interview and ISI score >7. Participants will also be administered a battery of self-report questionnaires selected to assess quality of life, daily functioning, disability, sleep, and subjective cognitive functioning, as well as a brief (45 min) standardized neuropsychological battery to pilot procedures for a larger trial. To reduce fatigue, participants will be offered and encouraged to take breaks as often as needed when appropriate. Participants will then complete a sleep diary for 14-days to prospectively record sleep and will be given an actigraph (a wearable activity/sleep monitor) to wear continuously for the 14-day baseline evaluation.

Sleep-SMART Treatment Phase (6 sessions virtual): A licensed clinical psychologist with experience delivering CBT-I will deliver the 50-minute 6-session Sleep-SMART intervention via secure home-based video teleconferencing (e.g., Veteran Video Connect or Webex). Throughout the treatment phase, Veterans will be asked to keep a sleep diary as part of treatment. Missed and rescheduled appointments will be allowed, however we will limit total treatment completion time to 8 weeks from the first treatment session.

Post-treatment Assessment (2 hours in person): After completing the treatment, all Veterans will fill out a sleep diary and wear an actigraph for the 14-day post-treatment evaluation. Veterans will also be scheduled for a post-treatment assessment that will include completion of a) self-report questionnaires, b) neuropsychological testing, and c) a brief semi-structured interview.

Measures

Self-report measures of quality of life, daily functioning, disability, sleep, and cognition : WHO Disability Assessment Schedule 2.0 (WHODAS 2.0); Independent Living Skills Survey (ILSS); Quality of Life Inventory (QOLI); Neuro-QOL scales: Applied Cognition Executive Functions Scale and Applied Cognition General Concerns Scale; Everyday Cognition Scale (ECog); Sleep Diaries; Actigraphy; Insomnia Severity Index (ISI); Pittsburgh Sleep Quality Index (PSQI); Hopkins Verbal learning Test Revised (HVLT-R); Brief Visuospatial Memory Test-Rev (BVMT-R); Wechsler Adult Intelligence ScaleIV (WAIS-IV) Digit Span; DKEFS Trails (Number and Letter Sequencing & Number-Letter Switching); D-KEFS Verbal Fluency.

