Feasibility: Feasibility in this investigation will be measured by: 1) **Recruitment:** absolute number, proportion, and representativeness of individuals willing to participate, documenting the utility of recruitment strategies, recording reasons for not participating, and noting challenges in meeting inclusion /exclusion criteria; 2) **Accrua**l: estimated as the number of patients accrued divided by the number of months of accrual; 3) **Refusal Rate:** estimated as the number of patients who refuse to participate divided by the number eligible; 4) **Retention:** defined as the percentage of Veterans who complete the 6-session treatment; 5) Participants who drop out will be contacted via telephone to document **Reasons for**

Treatment Discontinuation; 6) **Treatment Fidelity:** Therapist Checklist; 7) Feasibility of Intervention Measure (FIM) completed by study therapists at post-intervention; and 8) **Periodic Reflections** in which the research team will engage in guided monthly discussions, using the template provided by Finley et al. 2018, to ensure consistent documentation of key activities and other phenomena, e.g., barriers and facilitators

Acceptability: Acceptability in this investigation will be measured by collecting the following data from Veteran participants: 1) client Satisfaction Questionnaire (post-treatment); 2) **Percent of sessions attended;** 3) **Treatment adherence**: percent homework completion, basic skills assessment of treatment material, and discrepancy scores between prescribed sleep time and objectively recorded sleep; 4) **Telehealth Usability Questionnaire** (TUQ); and 5) **Semi-Structured Interview** in which a trained clinical research staff member will conduct a 20-minute audio-recorded, post-intervention semi-structured qualitative interview which will involve administration of the Acceptability of Intervention Measure (AIM) and Intervention Appropriateness Measure (IAM) followed by the collection of qualitative data for each of these scales as well as additional information regarding barriers, facilitators, etc., to inform refinements to the intervention and to inform future delivery and scale up of Sleep-SMART via telehealth.

Data Analytic Plan

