Participants without access to a smartphone, tablet, or computer with webcam will be given a loaner tablet for the 6-session treatment phase, which are available through Co-I [name]'s lab, purchased through VA mobile. The tablets are FIPS 140-2 encryption validated and listed in the VA EIL. The tablets will be used for the video-based Sleep-SMART sessions. No data will be stored on the tablets, but a video recording of each session will be stored on the VA network.
Those who participate in the Sleep-SMART treatment will be given an Actiwatch Spectrum (Philips Respironics, Bend, OR) to wear for 2 week prior to treatment and for two weeks after completing the treatment. The Actiwatch is a wrist-watch styled device designed to objectively measure levels of activity, sleep, and illumination exposure. The actiwatches are FIPS 140-2 encryption validated and listed in the VA EIL. Data (i.e., sleep, activity, and light exposure information) collected from the actiwatches will be transferred from the watches and stored on the VA network.
27.2c) Does the study require use of an electronic data capture system?
⊙ Yes ○ No
27.2c1) Provide the web address, details regarding their security features, the nature of the data involved, and the research purpose. Also include a description of how VA retains a copy of the data entered into the system.
The secure VA eScreening program may be used to collect some self-report questionnaire data.

VA approved software (e.g., ATLAS.ti) may used to analyze qualitative data.
SPSS 26.0 will be used to analyze quantitative data.
We will use the Actiwatch Spectrum (Philips Respironics, Bend, OR): a wrist-watch styled device designed to objectively measure levels of activity, sleep, and illumination exposure. Use of the Actiwatch will allow us to objectively measure sleep and wake activity during the baseline and post-treatment assessment weeks.
The data entered into these systems will be exported by research staff and stored within the VA secure network in the PI's folder in the R drive.
27.2d) Will any other web-based applications be used (e.g., for recruitment, completing online questionnaires, or processing data)?
O Yes ⊙ No
27.2e) Will coded data that excludes personal identifiers be used? Coded data excludes all HIPAA identifiers (per VHA Handbook 1605.1 Appendix B), including dates
⊙ Yes ○ No
27.2e1) Identify where the code key is stored and in what format (electronic, paper).

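### The objective sleep-discrepancy score listed as treatment adherence has no actigraphy from the treatment phase, so as scheduled it can describe only maintenance afterwards

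*Protocol*

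**What the plan says.** H2 in Protocol Section 6 lists treatment adherence among the measures of acceptability, and one of its three components is "discrepancy scores between prescribed sleep time and objectively recorded sleep". The Acceptability paragraph of Section 9 repeats the item in the same words. The other two components are homework completion and a skills check. Session attendance is listed separately.

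The recording schedule is in Section 9. At baseline, Veterans keep a diary and wear an actigraph for 14 days. During treatment the only sleep record described is the diary: "Throughout the treatment phase, Veterans will be asked to keep a sleep diary as part of treatment". Afterwards, "After completing the treatment, all Veterans will fill out a sleep diary and wear an actigraph for the 14-day post-treatment evaluation". On the length of the treatment phase, the protocol says that "we will limit total treatment completion time to 8 weeks from the first treatment session".

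Section 27.2 gives the same two windows twice. The device is given to Veterans "to wear for 2 week prior to treatment and for two weeks after completing the treatment" (27.2b1), and its purpose is to "objectively measure sleep and wake activity during the baseline and post-treatment assessment weeks" (27.2c1). The Measures list in Section 9 names both instruments: "Sleep Diaries; Actigraphy; Insomnia Severity Index (ISI").

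Section 15 places sleep restriction in the early treatment sessions. The SAP does not mention the discrepancy score. Neither document says which nights it uses, which prescription it is compared with, or how it is calculated.

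**The concern.** A discrepancy between prescribed and recorded sleep needs two things for the same night: a prescription that applies, and a recording. The protocol asks for an objective recording but schedules none during the period when the prescription is being given and followed.

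This matters because adherence is central to the pilot. Section 7 gives keeping Veterans with cognitive impairment adherent to the CBT-I regimen as the purpose of adding the CogSMART strategies. The SAP (General data considerations) names adherence, with feasibility and acceptability, as something the pilot tests in preparation for larger trials. A score labelled treatment adherence but built only from later nights could mislead in either direction. A good value could follow poor adherence during treatment, and a poor value could reflect relaxation once sessions had ended.

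**Working it through.** The documents give no figure to reproduce. The check is a count of nights.

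**Inputs**
- Baseline actigraphy: 14 days, before treatment (Section 9, Pre-Treatment Assessment; 27.2b1).
- Post-treatment actigraphy: 14 days, after treatment (Section 9, Post-treatment Assessment; 27.2b1).
- Treatment phase: length L nights, not fixed, with a ceiling of 8 weeks × 7 = 56 nights (Section 9).
- Sleep restriction: begins inside the treatment phase (Section 15).

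**Step 1. Scheduled actigraphy nights per Veteran.** 14 + 14 = 28.

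**Step 2. Overlap with treatment.** Number treatment nights 1 to L. Baseline nights are then −14 to −1, and post-treatment nights are L+1 to L+14 at the earliest. Neither set shares a night with 1 to L, so the overlap is 0 for every L. Trial values give the same answer:

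| L (nights) | Actigraphy nights in treatment | Total actigraphy nights |
|---|---|---|
| 35 (assumed) | 0 | 28 |
| 42 (assumed) | 0 | 28 |
| 56 (ceiling) | 0 | 28 |

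**Step 3. Nights that could be paired with a prescription.** The 14 baseline nights precede any prescription, which leaves 28 − 14 = 14, all after treatment.

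**Step 4. Is there a prescription on those 14 nights?** Neither document says that one still applies once treatment has ended. The 14 is therefore a maximum, reached only if a comparator such as the last prescription is adopted and recorded.

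The result that matters is the zero in Step 2, which does not depend on L. The 56 is a scheduling limit that allows for missed and rescheduled sessions. It is not a count of prescription nights: Section 15 describes safety planning at the session before restriction starts, so some treatment nights have no restriction prescription under any design.

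**The case against.** **A post-treatment score may be what was meant.** H2 never says that the score uses treatment nights, so the sections do not contradict each other outright. This stands, and it rules out the stronger reading that the score cannot be computed. It does not rescue the label, because both places call the score treatment adherence and neither document defines its nights or its comparator.

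**Treatment-phase adherence is measured in other ways.** Attendance, homework completion and the skills check all draw on the treatment phase. Homework is not itemised and may include following the sleep schedule. This also stands. A reader might infer that H2 has no adherence information from treatment, or none that touches on sleep, and the documents do not support either inference. What is missing is a defined comparison of recorded sleep with the prescription on treatment nights.

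**Veterans who stop early.** A reader might infer that they will all lack the score, since post-treatment wear is described as following completion and the dropout contact is by telephone ("Participants who drop out will be contacted via telephone to document" reasons). The documents do not settle this. The SAP plans to analyse whoever provides outcome data, whatever their compliance, which allows for non-completers giving data. No number of Veterans without a score can be derived.

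**This is a small descriptive pilot.** No test, threshold or progression rule uses the score, and the SAP disclaims efficacy testing. This is correct, and it limits the severity.

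**A diary score is not objective.** This is true, and the remedy has to say so. The diary is nevertheless the only nightly sleep record planned during treatment.

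**Conclusion.** The point holds. As scheduled, the discrepancy score contains 0 actigraphy nights from the treatment phase and at most 14 usable nights per Veteran, all after treatment. It can show whether a prescription was maintained afterwards, if one is taken to apply. It cannot show adherence while the regimen is being delivered.

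This rests on two readings: that the actigraph is the only objective sleep recorder, and that the windows in Sections 9 and 27.2 are complete. The sections agree with each other, and nothing elsewhere adds a device or a wear period.

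Severity is modest, but the change is worth making because adherence is a stated target of the pilot and the remedy is cheap. Confidence is high for the night count. It is lower for the effect on interpretation, which depends on how the investigators meant to use the score.

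**What to change.** 1. **Add a treatment-phase score.** Compare diary time with the prescription in force, on nights that have one, for every Veteran given a prescription. State which diary quantity is compared. Report signed and absolute differences, since the absolute value alone hides whether a Veteran ran over or under, and give the number of scored nights per Veteran. Record each prescription with its start date.
2. **Keep the actigraphy comparison and define it.** State that it uses the post-treatment fortnight and which prescription it is compared with. Label it post-treatment maintenance in Section 6 (H2), in Section 9 (Acceptability) and in the SAP.
3. **Report how many Veterans have each score,** showing non-completers separately.

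**Cost.** Wording in both documents, plus retention and entry of the treatment diaries and prescription dates. The protocol describes those diaries as part of treatment and does not say that they are kept as research data, so this work is additional. No new device or visit is needed.

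**Limits.** The treatment-phase score is self-reported by people with MCI, and it does not supply objective treatment-night data. Those would require actigraph wear during treatment. Continuous wear would add up to 56 nights, for a ceiling of 28 + 56 = 84 per Veteran, and fewer if treatment is shorter or only prescription nights are recorded.

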Cognitive Behavioral Therapy for Insomnia (CBT-I) is the first-line treatment for chronic insomnia. However, cognitive impairments may limit progress in CBT-I for older Veterans with Mild Cognitive Impairment (MCI). This study will develop and pilot test Sleep-SMART (Sleep Symptom Management and Rehabilitation Therapy), an adapted CBT-I treatment that incorporates Cognitive Symptom Management and Rehabilitation Therapy (CogSMART) principles with a goal of improving sleep treatment and rehabilitation outcomes for Veterans with co-occurring MCI and insomnia. The innovation of this study centers on enhancing CBT-I by providing supportive cognitive strategies designed to improve treatment adherence, learning, and acceptability. We anticipate that by improving sleep we can concurrently improve daily functioning, increase quality of life, prevent or reduce late-life disability, and mitigate longterm cognitive decline in this Veteran population.

Section 6 - Specific Aims

6) Provide a statement of specific aims and hypotheses that serve as the basis for this protocol. Emphasize those aspects that justify the use of human subjects.

Aim 1: Develop the Sleep-SMART intervention and treatment manual using a participatory research approach during a 6-month development phase.

Aim 2: Assess the feasibility and acceptability of Sleep-SMART in 26 Veterans aged 60 or older with MCI and insomnia.

H1: Feasibility. 26 Veterans will be enrolled. At least 20 Veterans will complete the treatment. Feasibility will also be assessed by collecting data on recruitment; refusal rate; reasons for treatment discontinuation; treatment fidelity; and tracking contextual barriers and facilitators for implementation.

H2: Acceptability. Veterans will find Sleep-SMART acceptable as measured by the Client Satisfaction Questionnaire (CSQ); Acceptability of Intervention Measure (AIM) and Intervention Appropriateness Measure (IAM); qualitative interview data; percent of sessions attended; and treatment adherence (percent homework completion, basic skills assessment of treatment material, and discrepancy scores between prescribed sleep time and objectively recorded sleep).

Aim 3: We will explore the effects of Sleep-SMART on rehabilitation outcomes (WHODAS 2.0, ILSS), quality of life (QOLI), sleep (PSQI, ISI, sleep efficiency), and cognitive functioning (subjective: Neuro-QOL and ECog; objective: neuropsychological assessment).

Section 7 - Background and Significance

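### AIM and IAM are given inside a staff-led, recorded interview with no stated provision for private completion, which leaves two of the H2 acceptability ratings open to courtesy bias.

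*Protocol*

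**What the plan says.** Section 6 of the protocol states H2 as "Veterans will find Sleep-SMART acceptable as measured by the Client Satisfaction Questionnaire (CSQ); Acceptability of Intervention Measure (AIM) and Intervention Appropriateness Measure (IAM", and then adds qualitative interview data, percent of sessions attended and treatment adherence. Adherence covers homework completion, a skills assessment and "discrepancy scores between prescribed sleep time and objectively recorded sleep". No measure is ranked above another, and no cut-off is given for any of them.

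Section 9, Acceptability, item 5 sets out how AIM and IAM are collected. The setting is a session of 20 minutes, held after treatment, run by trained clinical research staff and recorded on audio. Of its content the protocol says: "which will involve administration of the Acceptability of Intervention Measure (AIM) and Intervention Appropriateness Measure (IAM) followed by the collection of qualitative data". That follow-up covers both scales. The CSQ and the Telehealth Usability Questionnaire are separate items in that list. Only AIM and IAM are folded into the interview.

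The Post-treatment Assessment paragraph of Section 9 describes one in-person visit with three components: "a) self-report questionnaires, b) neuropsychological testing, and c) a brief semi-structured interview". Section 27.2 adds that "The secure VA eScreening program may be used to collect some self-report questionnaire data". AIM and IAM are not named there.

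The SAP does not mention AIM or IAM. They fall under its general statement that all quantitative variables will be described.

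**The concern.** A rating of how acceptable a treatment is depends on the respondent feeling free to mark it down. Here the Veteran has just finished a free course of individual therapy and gives the rating during a conversation with study staff that is being recorded and will turn to that same rating. This is a familiar setting for courtesy, or social-desirability, bias.

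Two features of the plan limit its ability to cope with such bias. All 26 Phase II participants receive Sleep-SMART, so no comparison group would carry the same shift and cancel it. The analysis of these scales is descriptive, so the observed mean is itself the evidence offered for this part of H2. The SAP also says the pilot is meant to try out the measurements for a later large trial, so a weak collection procedure could be carried forward.

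**Working it through.** The plan contains no figure on this point to reproduce. The main check is to set the texts side by side.

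1. **Mode of completion.** Item 5 speaks of administering the scales. Elsewhere in Section 9 the same verb is used for self-report forms: "Participants will also be administered a battery of self-report questionnaires". The therapists' scale is worded differently: "Feasibility of Intervention Measure (FIM) completed by study therapists at post-intervention". The wording therefore does not settle whether AIM and IAM items are read aloud or marked on a form.
2. **Does the mode matter to the point?** If items are read aloud, the rating is spoken to the interviewer. If a form is handed over, it is completed within a session run by that person, who then asks about each scale. Neither version is described as private. Leaving the mode open also allows it to differ between Veterans.
3. **Is there another place for the scales?** Yes. The same visit already has a self-report component, listed separately from the interview.
4. **Is there an independent check?** The mixed-methods plan uses qualitative data to explain, support or contradict the quantitative data. For these two scales, the scale-specific qualitative data come from the same interviewer and sitting, so both could share the same bias.
5. **Do existing safeguards reach the problem?** Section 12.1 says participants may skip questions and that their information will not affect their care. Sections 9.11 and 15 limit identification on recordings to a project ID. These protect voluntariness and confidentiality. They do not hide the rating from the person in the room.

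**Illustration of scale, under assumption.** Inputs: n = 20 (the H1 completion target) and n = 26 (planned enrolment), both from Section 6. The constant upward shift *b*, in between-Veteran SD units, is assumed, and ratings are treated as roughly normal. The plan does not specify a confidence interval for AIM or IAM; one is used here only as a yardstick.

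- Standard error of a mean in SD units: 1/√n = 0.224 (n = 20) and 0.196 (n = 26).
- 95% half-width: t(0.975, n−1)/√n = 0.468 SD (n = 20) and 0.404 SD (n = 26).
- Coverage of the true mean: P(−c ≤ T ≤ c), with c = t(0.975, n−1) and T noncentral t on n−1 degrees of freedom with noncentrality b√n.

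| Assumed shift b (SD) | b√n, n = 20 | Coverage, n = 20 | b√n, n = 26 | Coverage, n = 26 |
|---|---|---|---|---|
| 0 | 0 | 0.950 | 0 | 0.950 |
| 0.2 | 0.89 | 0.864 | 1.02 | 0.835 |
| 0.3 | 1.34 | 0.753 | 1.53 | 0.687 |
| 0.5 | 2.24 | 0.435 | 2.55 | 0.312 |

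The column b√n is the shift in standard errors. The table shows what a shift of a given size would do. It is no evidence that such a shift occurs in this trial.

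**The case against.** The strongest reply is that this is a sensible mixed-methods choice in a small descriptive pilot. Asking about each rating straight after it is given helps to explain it, and probing may draw criticism out as well as suppress it. Some Veterans with MCI may do better with staff at hand. Several H2 measures, such as attendance and the sleep-time discrepancy, are not opinions and cannot be raised by politeness to an interviewer. No pass mark exists for AIM or IAM, no efficacy test is planned, and the SAP promises cautious interpretation. Much of this stands and it limits the weight of the point. It does not remove it: the behavioural measures do not record what the Veteran thinks of the treatment, and completing the scales first keeps the follow-up discussion intact.

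A reader might also infer more than the documents support:

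- **That ratings are spoken aloud on tape.** This is possible but not stated, as step 1 of the working shows.
- **That the interviewer may be the treating clinician or helped develop the treatment.** Nothing in the text says so, and different terms are used for the two roles: a licensed clinical psychologist delivers sessions, and a clinical research staff member interviews. The staff descriptions called for by Section 21 are not in the available text, so silence there cannot be counted against the plan.
- **That AIM and IAM are the key ratings.** H2 ranks nothing.
- **That the format is known to raise scores.** The documents give neither a direction nor a size.
- **That a shift could turn H2 from failed to met.** With no threshold, there is no line to cross.

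**Conclusion.** The point holds as a modest one. The plan collects two of several unranked acceptability ratings in a setting that invites courtesy answers, states no provision for private completion, and leaves the mode unspecified. In a single arm, a constant shift would be invisible and could not be corrected afterwards.

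The size is unknown. The coverage figures rest wholly on assumed shifts of 0.2 to 0.5 SD, with 20 to 26 respondents and roughly normal ratings. No formal decision in the plan depends on these scales. The conclusion is that the bias cannot be ruled out and is cheap to reduce, not that the ratings will be wrong.

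**What to change.** In Section 9, move AIM and IAM from the interview to the self-report component of the same post-treatment visit. State that each Veteran completes them privately, on paper or in VA eScreening, under the project ID and before the interview begins. The order needs stating, because the current list of visit components does not fix one. Keep the interview for the open questions on each scale, so that the qualitative follow-up is unchanged.

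Some Veterans may need help reading the items. Record assisted completion for each participant, and have the SAP report how many ratings were assisted. Private completion should be workable for most: the inclusion criteria already require participants to read English, and the protocol already asks them to fill in other questionnaires and sleep diaries.

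The cost is a change of order within one visit and one extra data field, with no new visit or instrument. The change lowers the risk without abolishing it, since Veterans may still expect to discuss their ratings.
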